# **Renal Impairment**

If subsequent to study entry and while still on study therapy, a patient's estimated CrCl falls below the threshold for study inclusion ( $\geq$ 51 ml/min), retesting should be performed promptly.

A dose reduction is recommended for patients who develop moderate renal impairment (calculated creatinine clearance by Cockcroft-Gault equation or based on a 24 hour urine test of between 31 and 50 ml/min) for any reason during the course of the study: the dose of olaparib should be reduced to 200 mg twice daily.

Because the CrCl determination is only an estimate of renal function, in instances where the CrCl falls to between 31 and 50 mL/min, the investigator should use his or her discretion in determining whether a dose change or discontinuation of therapy is warranted.

Olaparib has not been studied in patients with severe renal impairment (creatinine clearance  $\leq 30$  ml/min) or end-stage renal disease; if patients develop severe impairment or end stage disease it is recommended that olaparib be discontinued.

# 9.0 ADVERSE EVENTS: LIST AND REPORTING REQUIREMENTS

#### 9.1 Definitions

## 9.1.1 Adverse Event (AE)

An adverse event is the development of an undesirable medical condition or the deterioration of a pre-existing medical condition following or during exposure to a pharmaceutical product, whether or not considered causally related to the product. An undesirable medical condition can be symptoms (e.g., nausea, chest pain), signs (e.g., tachycardia, enlarged liver) or the abnormal results of an investigation (e.g., laboratory findings, electrocardiogram). New medical conditions / diseases occurring before starting the study treatment but after signing the informed consent form will not be recorded as AEs. Additionally, expected progression of the disease being studied will not be recorded as an adverse event. In clinical studies, an AE can include an undesirable medical condition occurring at any time, including run-in or washout periods, even if no study treatment has been administered.

The term AE is used to include both serious and non-serious AEs.

# 9.1.2 Serious Adverse Event (SAE)

The investigator must assess each event to determine if it meets the criteria for classification as an SAE or serious adverse drug reaction.

All SAEs (including death) occurring from the first dose study drug, throughout the study, and 30 days after the last dose of study drug or before initiation of a new antineoplastic treatment (whichever comes first) must be reported. All SAEs that the investigator considers related to the study drug occurring after the follow-up periods must be reported.

A serious adverse event is an AE occurring during any study phase (i.e., screening, run-in, treatment, wash-out, follow-up), at any dose of the study drugs that fulfills one or more of the following criteria:

- Results in death
- Is life threatening (defined as an event in which the subject was at risk of death at the time of the event; it does not refer to an event which hypothetically might have caused death if it were more severe)
- Requires inpatient hospitalization or causes prolongation of existing hospitalization (see note below for exceptions) for >24 hours
- Results in persistent or significant disability or incapacity
- Is a congenital anomaly/birth defect (note: reports of congenital anomalies/birth defects must also be reported on the Pregnancy Form)
- Is an important medical event (defined as a medical event(s) that may not be immediately life-threatening or result in death or hospitalization but, based upon appropriate medical and scientific judgment, may jeopardize the subject or may require intervention [e.g., medical, surgical] to prevent one of the other serious outcomes listed in the definition above.) Examples of such events include, but are not limited to, intensive treatment in an emergency room or at home for allergic bronchospasm; blood dyscrasias or convulsions that do not result in hospitalization), potential drug induced liver injury, hemophagocytic lymphohistiocytosis
- Suspected transmission of an infectious agent (e.g., pathogenic or nonpathogenic) via the study drug is an SAE.
- Is a new cancer that is not a condition of the study (see clarification below)
- Is associated with an overdose

Events **not** considered to be SAEs are hospitalizations for:

- Admissions as per protocol for a planned medical/surgical procedure or to facilitate a procedure
- Routine health assessment requiring admission for baseline/trending of health status (e.g., routine colonoscopy)
- Medical/surgical admission for purpose other than remedying ill health state and was planned prior to entry into the study. Appropriate documentation is required in these cases.
- Admission encountered for another life circumstance that carries no bearing on health status and requires no medical/surgical intervention (e.g., lack of housing, economic inadequacy, care-giver respite, family circumstances, administrative).
- Admissions for monitoring of treatment-related infusion reactions that do not otherwise meet the criteria for a SAE.

Hospitalization for chronic or long-term patients and inpatient admission also includes transfer within the hospital to an acute or intensive care inpatient unit. Prolongation of hospitalization is any extension of an inpatient hospitalization beyond the stay anticipated or required for the original reason for admission.

Of note, Adverse Events (AEs) for malignant tumors reported during a study should generally be assessed as Serious AEs.

The above instruction applies only when the malignant tumor event in question is a new malignant tumor (i.e., it is not the tumor for which entry into the study is a criterion and that is being treated by the IP under study and is not the development of new or progression of existing metastasis to the tumor under study). Malignant tumors that – as part of normal, if rare, progression – undergo transformation (e.g., Richter's transformation of B cell chronic lymphocytic leukemia into diffuse large B cell lymphoma) should not be considered a new malignant tumor.

The causality of SAEs (their relationship to all study treatment/procedures) will be assessed by the investigator(s) and communicated to AstraZeneca and McGuff.

### 9.1.3 Olaparib adverse events of special interest

Adverse events of special interest (AESI) are events of scientific and medical interest specific to the further understanding of olaparib's safety profile and require close monitoring and rapid communication by the investigators to AstraZeneca. Any AESI that occur should be reported using the form in **Appendix F**. An AESI may be serious or non-serious. Adverse Events of Special Interest for olaparib are the Important Potential Risks of MDS/AML, new primary malignancy (other than MDS/AML) and pneumonitis.

ANY event of MDS/AML, new primary malignancy, or pneumonitis should be reported to AstraZeneca Patient Safety whether it is considered a non-serious AE (e.g. non-melanoma skin cancer) or SAE, and regardless of investigator's assessment of causality or knowledge of the treatment arm.

A questionnaire will be sent to any investigator reporting an AESI, as an aid to provide further detailed information on the event. During the study there may be other events identified as AESIs that require the use of a questionnaire to help characterize the event and gain a better understanding regarding the relationship between the event and study treatment.

### 9.1.4 Progression of malignancy

Progression of a patient's malignancy should not be considered an AE, unless in the investigator's opinion, study treatment resulted in an exacerbation of the patient's condition. If disease progression results in death or hospitalization while on study or within 30 days of the last dose of study drug, progressive disease will be considered an SAE.

#### 9.1.5 Significant disability

Disability is a substantial disruption of the patient's ability to conduct normal life functions.

#### 9.1.6 Pregnancy

Male participants should refrain from fathering a child or donating sperm during the study and for 3 months following the last dose.

Pregnancy of the patient's partners is not considered to be an adverse event. However, the outcome of all pregnancies (spontaneous miscarriage, elective termination, ectopic pregnancy, normal birth or congenital abnormality) should if possible be followed up and documented.

The outcome of any conception occurring from the date of the first dose until 3 months *after the last dose* should be followed up and documented.

All outcomes of pregnancy should be reported to AstraZeneca and McGuff.

# 9.1.7 Medical Significance

An event that is not fatal or life-threatening and that does not necessitate hospitalization may be considered serious if, in the opinion of the investigator, it jeopardizes the patient's status and might lead to medical or surgical intervention to prevent any of the above outcomes. Such medically significant events could include allergic bronchospasm requiring intensive treatment in the emergency room or at home, blood dyscrasias that do not result in inpatient hospitalization, or the development of drug dependency or abuse.

#### **9.1.8 Deaths**

All deaths that occur during the study, or within the protocol-defined 30-day post-study follow-up period after the administration of the last dose of study treatment, must be reported as follows:

Death clearly the result of disease progression should be reported to the study monitor at the next monitoring visit and should be documented in the eCRF but should not be reported as an SAE.

When death is not due (or not clearly due) to progression of the disease under study, the AE causing the death must be reported to the study monitor as an SAE within **24 hours** (see **Section 9.5.1** for further details). The report should contain a comment regarding the co-involvement of progression of disease, is appropriate, and should assign main and contributory causes of death. This information can be captured in the 'death eCRF'.

Deaths with an unknown cause should always be reported as an SAE. A postmortem may be helpful in the assessment of the cause of death, and if performed a copy of the postmortem results should be forwarded to AstraZeneca and McGuff within the usual timeframes.

The NCI CTCAEv5.0 will be used for adverse event descriptions and grading.

Follow-up of adverse events should continue until the event and any sequel resolve or stabilize at a level acceptable to the investigator and the medical monitor.

Events that are **not** considered serious adverse events include:

- Routine treatment or monitoring of the studied indication, nor associated with any deterioration in condition, or for elective procedures
- Elective or pre-planned treatment for a pre-existing condition that did not worsen emergency outpatient treatment for an event not fulfilling the serious criteria outlined above and not resulting in inpatient admission
- Respite care

# 9.2 Expectedness

Adverse events can be considered, "expected", or "unexpected".

#### 9.2.1 Expected Adverse Events

Expected adverse events are those that have been previously identified as resulting from administration of the agent. An adverse event can be considered expected when it appears in the current adverse event list, the Investigator's Brochure, the package insert or is included in the informed consent document as a potential risk.

# 9.2.2 Unexpected Adverse Events

An adverse event can be considered unexpected when it varies in nature, intensity or frequency from the information provided in the current adverse event list, the Investigator's Brochure, the package insert or when it is not included in the informed consent document as a potential risk. Contact the lead site, Principal Investigator or sponsor to confirm unexpected adverse events when necessary.

# 9.3 Recording and Grading

#### 9.3.1 Recording

All adverse events, regardless of treatment group, severity, suspected causal relationship, expectedness, or seriousness will be documented.

A clinically significant change in a physical examination finding or an abnormal test result (i.e. laboratory, x-ray, EKG) should be recorded as an AE if it:

- Is associated with accompanying symptoms
- Requires additional diagnostic testing or medical or surgical intervention
- Leads to a change in study dosing or discontinuation from the study
- Requires additional concomitant drug treatment or other therapy, or
- Is considered clinically significant by the investigator or sponsor

An abnormal test result that is subsequently determined to be in error does not require recording as an adverse event, even if it originally met one or more of the above criteria.

The following factors should also be considered:

- The temporal sequence from study drug administration The event should occur after the study drug is given. The length of time from study drug exposure to event should be evaluated in the clinical context of the event.
- Underlying, concomitant, intercurrent diseases Each report should be evaluated in the context of the natural history and course of the disease being treated and any other disease the subject may have.

- Concomitant medication The other medications the subject is taking or the treatment the subject receives should be examined to determine whether any of them might be recognized to cause the event in question.
- Known response pattern for this class of study drug Clinical and/or
  preclinical data may indicate whether a particular response is likely to be a
  class effect.
- Exposure to physical and/or mental stresses The exposure to stress might induce adverse changes in the recipient and provide a logical and better explanation for the event.
- The pharmacology and pharmacokinetics of the study drug The known pharmacologic properties (absorption, distribution, metabolism, and excretion) of the study drug should be considered.

### 9.3.2 Grading Severity

The investigator will make an assessment of grade for each AE and SAE reported during the study, which will be recorded in the eCRF. The assessment will be based on the National Cancer Institute's CTCAE (Version 5.0):

- Grade 1: Mild; asymptomatic or mild symptoms; clinical or diagnostic observations only; intervention not indicated
- Grade 2: Moderate; minimal, local or noninvasive intervention indicated; limiting age-appropriate instrumental activities of daily living
- Grade 3: Severe or medically significant but not immediately lifethreatening; hospitalization or prolongation of hospitalization indicated; disabling; limiting self-care activities of daily living
- Grade 4: Life-threatening consequences; urgent intervention indicated
- Grade 5: Death related to AE

Any AE that changes in grade during its course will be recorded in the eCRF at the highest level experienced by the subject. For example, if a patient experiences a Grade 2 AE that worsens to Grade 3, Grade 3 would be recorded for the entire duration of the event in the eCRF.

# 9.3.3 Attributing Causality

The relationship of an AE to the administration of the study drug is to be assessed by the investigator according to the following definitions:

- No (unrelated, not related, no relation): The time course between the administration of study drug and the occurrence or worsening of the adverse event rules out a causal relationship and another cause (concomitant drugs, therapies, complications, etc.) is suspected.
- Yes (related): The time course between the administration of study drug and the occurrence or worsening of the adverse event is consistent with a causal relationship and no other cause (concomitant drugs, therapies, complications, etc.) can be identified.

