#### 3.0 STUDY DESIGN

This is a multi-center phase II study to evaluate the safety and clinical activity of the combination of olaparib and high-dose IV ascorbate, as second or later line of therapy, in castration resistant prostate cancer patients with no known DNA repair gene mutations (DDRm). In brief, the primary endpoint is  $PSA_{50}$  response, defined by a 50% reduction in PSA from baseline. The secondary endpoints are assessing the PSA doubling time, radiographic and PSA PFS, safety and tolerability as defined by the incidence of grade 3 to 5 toxicities, and measuring overall survival. For complete endpoint definitions, see **Sections 13.2-13.4**. The total accrual for this clinical trial will be 12 men with castration resistant prostate cancer (n=12).

Olaparib will be administered at 300 mg PO BID; ascorbate will be administered at 1 g/kg IV twice weekly at least 24 hours apart until objective disease progression or unacceptable toxicities or patient withdrawal for other reasons.

The study will consist of a screening period (within 28 days of the first dose), treatment period, and follow-up period. Dose reductions are allowed per **Section 8.2.** Enrollment will continue until 15 subjects (allows for 3 drop outs) have received at least one dose of study treatment.

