# 8.0 DOSING DELAYS/MODIFICATIONS

# 8.1 Dosing Delays

All scheduled cycles occur over a 28-day period. If necessary, treatment may be delayed for up to 4 weeks. If treatment is delayed more than two weeks, the Principal Investigator must be contacted for further instructions on continued treatment. Additional delays or modifications to the treatment schedule must be approved by the Protocol Chair. When the delay is due to toxicity, then the next cycle may begin with a dose reduction.

Ascorbic acid will be withheld for the following drug-related toxicities:

- $Cr \ge 1.6 \times ULN$  (for patients with  $Cr \ge 1.6 \times ULN$ , calculated or measured creatinine clearance must be  $\ge 50 \text{ mL/minute}$  (Cockcroft-Gault))
- Common Terminology Criteria for Adverse Events (CTCAE) Grade 3 or 4 non-hematologic toxicity excluding asymptomatic electrolyte aberrations
- Any AE, laboratory abnormality, or intercurrent illness that, in the judgement of the investigator, warrants delaying the dose of study medication

Olaparib will be withheld for the following drug-related toxicities:

Absolute neutrophil count
 Platelets
 Hemoglobin
 Total bilirubin
 AST (SGOT)/ALT(SGPT)
 ≤ 750/ mm³, see Table 8
 ≤ 8 hgb, If < 10, see Table 7

 ≥ 1.5XULN
 ≥ 2.5 x ULN (<5x ULN if with known liver m

• AST (SGOT)/ALT(SGPT)  $\geq 2.5 \text{ x ULN (<}5\text{x ULN if with known liver metastases}$  provided bilirubin is normal)

- Common Terminology Criteria for Adverse Events (CTCAE) Grade 3 or 4 non-hematologic toxicity excluding asymptomatic electrolyte aberrations
- Any AE, laboratory abnormality, or intercurrent illness that, in the judgement of the investigator, warrants delaying the dose of study medication

If dosing parameters for Ascorbic Acid are not met, study participants may continue with olaparib therapy. If dosing parameters for olaparib or are not met, study participants may continue with Ascorbic Acid therapy. Dose interruptions are allowed as required, for a maximum of 4 weeks. Patients who require an interruption in olaparib or ascorbic acid for >4 weeks due to toxicity must permanently discontinue study drug unless an exemption is granted by the protocol chair (Refer to section 13.6 for stopping rule). Where toxicity reoccurs following re-challenge with study treatment, then the patient should be considered for dose reduction or must permanently discontinue study treatment per investigator judgement.

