#### 8.2 Dose Modifications

Patients enrolled in this study will be evaluated clinically and with standard laboratory tests before and at regular intervals during their participation in this study as specified in **Section 7.3.1.** The NCI CTCAE v.5.0 will be used to grade adverse events.

At each study visit for the duration of their participation in the study, patients will be evaluated for adverse events (all grades), serious adverse events (SAEs), and adverse events that require study drug interruption or discontinuation.

Adverse events possibly related to either study drug must be resolved to grade 1 or baseline prior to resumption of dosing.

Patients who experience grade 3 of 4 toxicities (individually defined in **Section 8.1**) that are eligible for retreatment will be dose reduced. After a two-week dose delay, if the grade 3 or 4 toxicity resolves to grades 0-2 (grade 2 peripheral neuropathy must resolve to grade 1 if interfering with instrumental ADL), then the following dose reductions are to be applied.

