# 9.4 Handling of Expedited Safety Reports

In accordance with local regulations, the Protocol Chair or designee will notify investigators of all SAEs that are unexpected (i.e., not previously described in the IB), and related to olaparib and IV ascorbic acid. This notification will be in the form of an expedited safety report (ESR) that is to be faxed to the investigators and the study coordinators. Upon receiving such notices, the investigator must review and retain the notice with the IB and where required by local regulations, the investigator will submit the ESR to the appropriate IRB. The investigator and IRB will determine if the informed consent requires revision. The investigator should also comply with the IRB institutional guidelines for reporting any other safety information.

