# 13.3 Secondary Endpoint Definitions

- Safety and tolerability will be defined by frequency of the drug-related adverse events by grade as assessed by the NCI CTCAE Version 5.0, lab measurements, and vital signs.
- Radiographic progression will be defined as soft tissue disease progression by modified RECIST criteria 1.1 (baseline LN size must be >1.0 cm to be considered target or evaluable lesion) or by development of two or more new bone lesions not consistent with tumor flair for prostate cancer working group 3. Radiographic progression free survival (rPFS) is defined as the number of months from initiation of therapy to date of first radiographic progression, death from any cause, or last patient evaluation. Patients who have not progressed or died will be censored at the last date they were assessed and deemed progression-free.
- Time to PSA doubling from baseline is a time-to-event outcome. Time is measured from the initiation of therapy until the PSA has increased to 200% of baseline value, and confirmed with another measurement at least 4 weeks later, or death. The date of PSA doubling will be the first value recorded (not the confirmatory value).
- PSA PFS is defined as time to first PSA failure (two consecutive increases in PSA of 50% and ≥5 ng/mL above nadir) or death.
- OS is defined as the number of months from initiation of therapy to death due to any cause.

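### The two causality categories in Section 9.3.3 do not cover every event, so the drug-related safety endpoint in Section 13.3 will rest on inconsistent attribution

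*Combined protocol and SAP*

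**What the plan says.** Section 9.3.3 (Attributing Causality) has two categories, each made of two conditions joined by *and*.

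- **Related:** the time course fits the drug as a cause, and "no other cause (concomitant drugs, therapies, complications, etc.) can be identified".
- **Unrelated:** the time course "rules out a causal relationship and another cause (concomitant drugs, therapies, complications, etc.) is suspected".

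Several other places use the attribution or describe it differently:

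- Section 13.3 makes it part of a secondary endpoint: "Safety and tolerability will be defined by frequency of the drug-related adverse events by grade".
- Section 3.0 describes the same endpoint without a causality filter, as "safety and tolerability as defined by the incidence of grade 3 to 5 toxicities", and refers the reader to Sections 13.2-13.4 for the full definitions.
- Section 8.1 begins its lists of hold criteria with drug-relatedness, for example "Olaparib will be withheld for the following drug-related toxicities".
- Section 8.2 uses a different level: "Adverse events possibly related to either study drug must be resolved to grade 1 or baseline prior to resumption of dosing". The non-hematological toxicity text in Section 8.2.2.3 has a similar possibly-related sentence.
- The SAE form (Appendix B) and the AESI form (Appendix F) record Related or Unrelated separately for olaparib, for IV ascorbic acid and for the underlying disease.

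**The concern.** A causality scale with two categories has to place every event in one of them. This one does not, and the uncovered case is an ordinary one. Patients have metastatic castration-resistant cancer and may have had several earlier lines of therapy. Section 9.3.1 asks the investigator to weigh the disease, other illnesses and other medication for each report, so another cause will sometimes be identified even when the timing fits the drug.

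The two study drugs add a second route into the gap. Sections 7.9.1 and 7.9.2 list seven common effects for both: nausea, vomiting, diarrhea, loss of appetite, fatigue, dizziness and headache. If attribution is made per drug, as on the forms, each drug can serve as the other's alternative cause.

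The trial has one arm, and Section 4.2.8 says there are no clinical data on this combination in this disease. There is no control group to separate drug effect from disease, so the drug-related table depends entirely on investigator attribution. If that attribution has no defined answer for a class of events, the table partly reflects who filled in the form.

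**Working it through.** The plan gives no figure on this point, so the check is logical.

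**Step 1. Cross the two conditions.** Treat timing as compatible or incompatible, and another cause as present or absent.

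| Timing | Another cause | Meets *related*? | Meets *unrelated*? | Category |
|---|---|---|---|---|
| Compatible | Absent | Yes | No | Related |
| Compatible | Present | No (another cause exists) | No (timing does not exclude the drug) | None |
| Incompatible | Present | No | Yes | Unrelated |
| Incompatible | Absent | No | No (no other cause suspected) | None |

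Two of the four combinations have a category. The second row matters most for the endpoint. The fourth matters less for the count, since few readers would call such an event drug-related.

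**Step 2. Limit the claim.** The definition of unrelated speaks of a cause that is suspected; the definition of related speaks of one that can be identified. An event with compatible timing and a cause that is only suspected, not identified, still meets the definition of related. The gap in the second row is therefore confined to events with an identifiable alternative.

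**Step 3. Look for a rule that closes the gap.**
- Section 9.3.1 lists factors to weigh but adds no category and no tie-break.
- Section 13.8 says how to handle the same event occurring repeatedly (take the worst grade and the closest attribution). It has no default for an event that fits neither category.
- Section 8.2 and the non-hematological text in Section 8.2.2.3 use a possibly-related level that a yes/no scale defined as in Section 9.3.3 cannot express.
- Appendices B and F let an event be marked related to a drug and to the disease at once. Under Section 9.3.3, identifying the disease as a cause removes the event from *related*. The forms conflict with the definition, and they cover only SAEs and AESIs.

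None of these closes the gap.

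**Step 4. Trace it to the endpoint.** Section 13.3 counts drug-related events by grade. A second-row event enters or leaves that count according to which failed condition the investigator overlooks. Overlooking the condition on other causes gives *related*; overlooking the condition on timing gives *unrelated*. The text does not choose.

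**Step 5. Size.** The documents give no share of events that have both compatible timing and an identifiable alternative. The possible share therefore runs from none to all of the events with compatible timing, and the effect on the count cannot be narrowed from the text.

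**The case against.** The strongest reply is that the harm is limited because much of the safety plan does not depend on attribution. Section 9.3.1 documents all adverse events whatever the cause. Section 13.8 lists them individually, summarizes overall incidence and tabulates toxicity by type and grade. Section 9.5.1 sends all SAEs to the IND sponsor regardless of causality. No hypothesis test or go/no-go rule uses the related count. All of this stands, and it keeps the point to the reliability of one secondary endpoint and the consistency of the wording.

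Four stronger readings are tempting, and the documents do not support them.

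- *Common toxicities cannot be called related, so the endpoint is under-counted.* Such an event is still related when no other cause can be identified. Events in the gap fail *unrelated* as well, so a downward count is the likely direction under a literal reading of *related*, not a certainty.
- *Most expected toxicity falls in the gap, judging by Table 1.* Table 1 gives incidence in germline BRCA carriers, mainly with ovarian or breast cancer (193 and 62 of 298, or 255 of 298). It says nothing about how often a rival cause is present in this population.
- *The stopping rule is weakened.* Section 13.6 counts grade 3-4 adverse events that fail to resolve after four weeks off drug and cites Section 8.1. The citation most naturally refers to the four-week interruption, and the return reference in Section 8.1 sits in that paragraph. The text is not explicit, which justifies a clarification but no stronger claim.
- *Expedited reports and holds for fatigue, nausea or anemia will be missed.* Section 9.4 covers unexpected SAEs "related to olaparib and IV ascorbic acid", whereas these effects are listed as expected in Section 7.9.2. Tables 7 and 8 act on laboratory values or grade, with no relatedness filter, and Section 8.1 also leaves room for investigator judgement.

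**Conclusion.** The point holds as a defect of definition. Section 9.3.3 leaves two of four combinations without a category, nothing elsewhere repairs this, and Section 13.3 builds a secondary endpoint on the result. The supportable conclusion is that drug-related counts will be attributed inconsistently between investigators. A literal reading of *related* lowers them, by an amount the documents do not allow anyone to estimate.

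This rests on two assumptions: that investigators apply the definitions as written, and that some events will have both compatible timing and an identifiable alternative. The second is reasonable in metastatic disease with two drugs of overlapping toxicity, but it is not quantified. The primary endpoint, the decision rule of 2 or more responders in 12 and the all-cause tables are unaffected. The change should be made because it is cheap and the only count that tries to isolate drug effect depends on it.

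**What to change.** 1. In Section 9.3.3, make the categories exhaustive. *Related*: given the time course, there is a reasonable possibility that either study drug caused or contributed to the event, even if another cause is also possible. *Unrelated*: all other events.
2. State that the other study drug does not count as an alternative cause, and that marking the underlying disease as related on the Appendix B and F forms does not prevent marking a study drug as related.
3. Reconcile the relatedness wording in Section 8.1, Section 8.2 and the non-hematological text of Section 8.2.2.3 with this scale. Which clinical action follows is for the protocol team to decide.
4. In Section 13.3, report grade 3-5 events regardless of attribution beside the drug-related count. This brings it into line with Section 3.0 and uses tabulations already planned in Section 13.8.
5. In Section 13.6, state whether the monitored events are filtered by relatedness.

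The cost is protocol and case-report-form guidance wording, with no added data collection. The drug-related rate may look somewhat higher than under the present definition.
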